7.4 Sample Size and Power Calculation

The primary endpoint of the study is to establish that telehealth PC is equivalent to inperson PC in patient-reported QOL at week-24, as measured by the FACT-L. Although the primary endpoints in our previous studies assessed the change in FACT-L from baseline to week-12, we chose to focus on QOL at 24 weeks as the life-expectancy of patients with advanced lung cancer has increased over the last few years. In our most recent randomized trial of early integrated PC versus standard oncology care, we observed a 7.5 (SD = 17.0) point difference in the FACT-L at week-24 favoring the early integrated PC group. Thus, we chose a conservative equivalence margin of 4 points, which is slightly more than 50% of the previously observed advantage with early integrated PC compared to oncology care alone. As a 6-point difference in FACT-L score is considered the lowest range of a clinically meaningful difference, our equivalence margin would not reach the threshold of clinically meaningful difference in QOL between telehealth PC and in-person PC. 53 With 469 patients per group, we would have 95% power to establish the equivalence of telehealth PC compared to in-person PC on the FACT-L, with a two-sided alpha of 0.05, and an equivalence margin of 4 points. In our recent trial, we observed 25% missing data at 24 weeks. Therefore, we increased our sample size to 625 per group (total sample size = 1250 patients) to ensure we have adequate power to assess the equivalence of telehealth PC compared to in-person PC. Importantly, we chose to be conservative in estimating the sample size of this trial given the proposed testing of equivalence of telehealth PC to in-person PC on secondary outcomes as well as the planned subgroup analyses.

The proposed study will also have adequate power to assess for equivalence of telehealth PC compared to in-person PC in EOL communication and hospice length-of-stay. With a sample size of 1250, we will have 89% power, with a two-sided alpha of 0.05, to assess the equivalence of telehealth to in-person PC on patient-reported EOL communication with an equivalence margin of 8%, assuming the rate of EOL communication in the in-person PC group is 30% (based on our recent trial). With this sample size, we will also have 94% power to establish the equivalence of telehealth PC compared to in-person PC in hospice length-of-stay, with a two-sided alpha of 0.05, and an equivalence margin of 6

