Early palliative care (PC) integrated with oncology care in the outpatient setting improves quality of life (QOL), mood, illness understanding, and end-of-life (EOL) care among patients with advanced cancer and their caregivers. Therefore, early integrated PC has become the standard of care for patients with advanced cancer. However, a shortage of PC professionals and lack of capacity within cancer clinics are major barriers to wide-scale implementation of early integrated PC. Novel models of care delivery, such as telehealth videoconferencing, have the potential to increase access to and efficient utilization of limited PC resources in a patient-centered manner. In the REACH study, the evidence-based early integrated in-person PC model was adapted to a telehealth platform using secure videoconferencing, thereby enabling PC clinicians to provide virtual home visits and increase access to specialty services in a patient-centered manner. If the proposed study demonstrates that telehealth is as effective as (or superior to) in-person PC, such findings would address a major evidence gap between the data supporting early integrated in-person PC and lack of data regarding how to disseminate this care model most efficiently, equitably, and effectively.

2. Study Design

REACH is a multicenter randomized comparative effectiveness trial of early integrated telehealth versus in-person PC. 1250 patients with advanced non-small cell lung cancer (NSCLC) and up to 1250 of their caregivers were enrolled through 20 Palliative Care Research Cooperative (PCRC) designated institutions across the United States. The Massachusetts General Hospital (MGH) was the lead site for the study and the additional 19 PCRC institutions. Patients without willing or available caregivers were eligible to participate in the study. Patients were randomized in a 1:1 manner using blocked randomization, and randomization was stratified by enrolling site.

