Sample size calculations were performed to demonstrate equivalence with a margin of ±4 points on the FACT-L at week 24, assuming a standard deviation of 17.5 points and a between-group difference of 0 points. 469 patients per group would achieve 95% power at a 5% significance level using two one-sided, equal-variance t-tests. To account for an anticipated 33% missing data proportion at week 24 due to loss-to-follow-up, withdrawal, or death, enrollment of 625 per group (1250 total) was planned.

9. General Statistical Considerations

Statistical Software

All statistical analyses will be performed using SAS (SAS Institute Inc., NC, USA) and R (R Foundation for Statistical Computing, Vienna, Austria).

Analysis Population

The primary analyses will be conducted according to the intention-to-treat principle. All randomized patients will be included and analyzed in the group to which they were initially randomized, regardless of intervention adherence. To address intervention contamination introduced during the COVID-19 pandemic, sensitivity analyses will be conducted to ensure the validity of the study findings. These sensitivity analyses may include per-protocol analysis, contamination adjusted intention-to-treat analysis using instrumental variables, and inverse probability weighting analyses to provide robust statistical estimates for the primary and secondary outcomes in this trial.

Patient Disposition

The flow of patients through the study will be demonstrated using a flow diagram, consistent with the Consolidated Standards of Reporting Trials (CONSORT) statement. This diagram will display number of patients assessed for eligibility, the number of patients who enrolled and randomized in the study and the number of patients who were excluded or otherwise not enrolled. For enrolled patients, the study group allocation will be displayed, along with the number of patients who complete follow-up assessments at each time point. The number of patients in each group who were lost to follow-up or otherwise excluded from analysis will be displayed.

Baseline Characteristics

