Baseline characteristics including demographic information, smoking status, cancer type, comorbidities, and baseline PROs score will be summarized by intervention group using descriptive statistics and visual displays. Descriptive statistics for continuous variables will include the number of subjects, mean, standard deviation, median, first and third quartiles, and minimum and maximum values for the observed value. Frequencies and percentages will be calculated for categorical variables.

Adjustment of the Intervention Effect

The primary analyses for all outcomes will be unadjusted except when adjustment for baseline outcome values is pre-specified. For the primary outcome, a sensitivity analysis will evaluate the impact of adjustment for study site, the randomization stratification variable (n=20 sites). Adjustment for study site via a main effect or random effect will be considered. Small strata will be combined as needed to ensure numeric stability of model estimates.

For all outcomes, sensitivity analyses will adjust for baseline characteristics that are imbalanced between treatment groups, if needed. Imbalanced characteristics will be identified *a priori* by examining the distributions of baseline characteristics known to be associated with the primary and secondary outcomes by intervention group. Characteristics that are imbalanced to an extent that is considered clinically meaningful will be included as main effects.

Significance Level and Multiplicity Adjustment

Statistical significance testing for equivalence of the primary outcome will use two one-sided tests, each with a type I error rate of 0.05. The Benjamini-Hochberg false discovery rate (FDR) control approach will be used to interpret results of significance tests of secondary outcomes with an FDR of 0.15. Analyses of exploratory outcomes will not be adjusted for multiple comparisons, and presented results will emphasize estimates and confidence intervals.

Scoring of Patient-Reported Outcomes

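### The SAP's sample-size inputs do not give its stated 95% power: 33% missing leaves 419 per group, not 469, and with SD 17.5 power is then about 90%

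*SAP*

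**What the plan says.** SAP section 8 (Sample Size and Power Calculation) aims to show equivalence within 4 FACT-L points in either direction at 24 weeks. Its inputs are given as "assuming a standard deviation of 17.5 points and a between-group difference of 0 points". It states that "469 patients per group would achieve 95% power at a 5% significance level using two one-sided, equal-variance t-tests". The step from evaluable to enrolled patients is: "To account for an anticipated 33% missing data proportion at week 24 due to loss-to-follow-up, withdrawal, or death, enrollment of 625 per group". That makes 1250 patients in all.

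Protocol section 7.4 arrives at the same 469 evaluable, 95% power and 625 enrolled per group, but cites other inputs. On variability: "we observed a 7.5 (SD = 17.0) point difference in the FACT-L at week-24". On attrition: "In our recent trial, we observed 25% missing data at 24 weeks".

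Two other parts of the SAP bear on the calculation. Section 9 (Significance Level and Multiplicity Adjustment) says that the primary equivalence test "will use two one-sided tests, each with a type I error rate of 0.05". Section 9 (Missing Data) has the primary analysis use available data without imputation, so each missing week-24 score lowers the number analysed.

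**The concern.** Between the protocol and the SAP, the SD rose from 17.0 to 17.5 and the missing proportion from 25% to 33%. Each change should have raised the required enrolment or lowered the power, yet 469, 625 and 95% stayed the same. The SAP gives no reason for either change.

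This paragraph is the SAP's only justification of sample size, and it supports the primary test. Taken at face value, it understates the type II error by about half. It also sets a wrong benchmark for attrition: a trial that lost exactly 33% would appear to be on plan while sitting 469 − 419 = 50 evaluable patients per group below the number on which the power claim rests. Death is among the listed causes of missingness in this population, so the benchmark is likely to be used.

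**Working it through.** **Inputs.** Margin 4, true difference 0, equal-variance t-tests, 469 evaluable and 625 enrolled per group (SAP section 8); 0.05 for each one-sided test (SAP section 9); 1:1 allocation (SAP section 2). SD and missing proportion: 17.5 and 33% (SAP section 8), 17.0 and 25% (Protocol 7.4).

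**Formula.** With n per group and a true difference of 0, the normal approximation to the power of the two one-sided tests is

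power = 2Φ(4/SE − 1.645) − 1, where SE = SD × √(2/n).

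The exact figure for the t-tests averages over the sampling distribution of the pooled SD. It is given beside the approximation and differs by less than 0.1 percentage point.

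**Step 1: reproduce the plan's figures from the protocol's inputs.**
- SD 17.0, n = 469: SE = 17.0 × √(2/469) = 1.110; 4/1.110 = 3.603; 3.603 − 1.645 = 1.958; power = 94.98% (exact 94.95%). This is the stated 95%.
- 25% missing: 625 × 0.75 = 468.75, or 469. Conversely, 469/0.75 = 625.3.

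So 469, 625 and 95% agree with SD 17.0 and 25% missing.

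**Step 2: use the SAP's SD and keep n = 469.** SE = 17.5 × √(2/469) = 1.143; 4/1.143 = 3.500; 3.500 − 1.645 = 1.855; power = 93.65% (exact 93.6%). For 95% at SD 17.5 the exact calculation needs 499 per group (498 falls just short, at 94.99%).

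**Step 3: use the SAP's missing proportion.** 625 × (1 − 0.33) = 418.75, or 419 per group. Keeping 469 evaluable would need 469/0.67 = 700 enrolled per group. The 33% can be recovered only as an add-on: 625/469 = 1.33. A 33% increase in enrolment corresponds to 25% missing.

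**Step 4: use both SAP inputs.** SE = 17.5 × √(2/419) = 1.209; 4/1.209 = 3.308; 3.308 − 1.645 = 1.663; power = 90.4% (exact 90.3%).

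| SD | Evaluable per group | Power (exact) | Type II error |
|---|---|---|---|
| 17.0 | 469 (25% missing) | 94.95% | 5.05% |
| 17.5 | 469 (25% missing) | 93.6% | 6.4% |
| 17.0 | 419 (33% missing) | 92.1% | 7.9% |
| 17.5 | 419 (33% missing) | 90.3% | 9.7% |

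**Step 5: look for a reading that restores 95%.** A stricter 0.025 per side makes matters worse: at SD 17.5, 87.6% with 469 and 82.1% with 419. For scale only, 95% power with SD 17.5 and 33% missing would take 499/0.67 = 744.8, or 745 enrolled per group.

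**The case against.** The arithmetic is not in dispute; the objections concern how much it matters.

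- *If 33% is a slip for 25%, the 90% figure falls away.* Then 469 remain, and power is 93.6% at SD 17.5 or 95% at SD 17.0. This is a fair point, and the slip is the likeliest origin, but it is an inference. The SAP calls 33% a missing data proportion and lists its causes. Even under the slip reading, 95% is not reached at SD 17.5.
- *The SD change is minor.* It does cost only about 1.4 points on its own (94.95% to 93.6%). Most of the loss comes from the missing-data step.
- *The primary model adjusts for baseline FACT-L (SAP section 10), whereas the power statement is for t-tests.* Adjustment reduces the residual SD to SD × √(1 − r²), where r is the correlation between baseline and week 24. Neither document gives r. Taking r = 0.3, 0.4 and 0.5 as assumptions, power at SD 17.5 and 419 per group is about 93.2%, 95.1% and 97.0%. This stands as a limit on the practical consequence. It does not rescue the SAP's sentence, which claims 95% for t-tests.
- *The protocol does not expressly name 17.0 as its power input.* It reports 17.0 as observed in the most recent trial and says the highest SD from earlier studies was used. That 469 fits 17.0 is strong evidence but not proof, so the sponsor should confirm the SD.
- *Enrolment is described as complete, and the margin, model and decision rule are untouched.* This is true, and it is why the remedy is confined to wording.

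**Conclusion.** The concern holds. SAP section 8 does not deliver its stated power from its own inputs. As written, 625 enrolled with 33% missing leaves 419 per group, and power at SD 17.5 is 90.3%, so type II error is 9.7% against a stated 5%. If the 33% is a slip for 25%, power at SD 17.5 is 93.6%. The stated 95% is obtained only with SD 17.0 and 25% missing.

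These figures assume a true difference of 0, a margin of 4, equal-variance two one-sided t-tests at 0.05 each, equal allocation and no credit for baseline adjustment. About 90% is still good power, and adjustment would raise it. The error lies in the justification, and the two documents disagree on SD and attrition for the same sample size. It must be corrected because it is the power statement for the primary test.

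**What to change.** The sponsor should first confirm which SD and missing proportion were used to set the sample size, then correct SAP section 8 in one of two ways:

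1. If the protocol's inputs were used, restore them: SD 17.0, 25% missing, 469 evaluable of 625 enrolled per group, power about 95%.
2. If SD 17.5 and 33% missing are the real expectations, keep them and state 419 evaluable per group with power about 90%, giving the reason for the departure from Protocol section 7.4.

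If credit is wanted for the baseline-adjusted model, state the assumed correlation between baseline and week 24, with its source. A value of about 0.4 would bring 419 per group at SD 17.5 back to 95%.

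A dated entry in the SAP addendum would do, as was done for other changes. The cost is wording, and under the second option a less favourable stated power. Enrolment, margin and analysis do not change.

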5.3.3 In-Person Arm

Patients randomized to in-person PC will be scheduled for their first PC visit within four weeks of enrollment and then at least every four weeks thereafter until the patient is no longer coming into the clinic (i.e. due to enrollment in hospice) or death. PC visits will be scheduled on the same day as oncology visits unless the patient is agreeable to scheduling the PC visit on a different day. Joint visits with PC and oncology (with both clinicians seeing the patient together in one visit) are recommended but not required. PC clinicians may see patients more frequently than every four weeks at their discretion. If patients do not have a scheduled visit to the cancer center the PC clinician will contact them via telephone within four weeks of their prior appointment to conduct the visit. Patients admitted to rehabilitation or skilled nursing facilities who are still coming into the cancer clinic for oncology visits should continue to meet with PC at least every four weeks. Patients who are receiving hospice services but still coming into the cancer clinic for oncology visits should continue to meet with PC at least every four weeks. Patients scheduled to meet with PC clinicians who do not speak their native language will be seen in conjunction with an interpreter service used by the hospital or with a family member or friend who speaks the language. In-person PC visits will require a standard co-payment as per the patients' insurance requirements, and PC will bill for the services.

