5.3.4 Both Study Arms

PC clinicians will document all patient encounters (in-person, telehealth, or telephone) in the patient's medical records. They will also complete an electronic survey after each clinical encounter to note the topics addressed during each study visit and whether any caregiver was present (see Data Collection).

If participants on either arm miss their scheduled visit and it cannot be rescheduled within four weeks of their prior visit, the PC clinician will attempt to contact them via telephone within seven days from the missed visit to conduct a visit via telephone. The PC clinician will document the telephone calls in the health record. If the patient is unable to be reached by telephone, the PC clinician will document in the health record that the PC team has attempted to contact the patient, or they have left a voicemail asking for a return call if there are issues needing to be addressed. Patients surviving greater than 18 months will be permitted to decrease the frequency of PC visits as per the discretion of their PC and oncology teams.

While the study protocol entails every four-week patient contact with a PC clinician, a variety of uncontrollable factors may impact intervention delivery. Patient factors include a change in their cancer treatment schedule, cancellation of cancer treatment, or

fatigue that prohibits participation in a visit. Clinician factors include clinic delays leading to missed patient appointments and insufficient staffing, especially due to meetings and vacations. We will document missed contact as a minor violation and institute a corrective action plan if more than 15% of all planned patient contact with PC does not take place per study protocol at a study site.

If the standard practice of the participating PC service is to have the inpatient PC team follow patients who receive outpatient PC if they are admitted to a hospital, the inpatient PC team will follow this practice and see the patient during their hospitalization. If patients are admitted to the hospital and miss a scheduled PC visit, they will have four weeks from the date of discharge for their next in-person or telehealth visit.

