5.5.3 Ensuring Fidelity of Study Design, Training, and Intervention We will take several steps to ensure the fidelity of our study design, training, and intervention delivery. The table below depicts the steps we will take to ensure the fidelity of our study design and intervention training and delivery.

Table 3. Summary of methods for treatment fidelity

Types of Fidelity	Procedures to Ensure Fidelity	Fidelity Assessment
Study Design	 Intervention development based on a well-defined conceptual model and systematic review of literature Standardization of intervention dose with clear feasibility data based on prior work Minimization of cross contamination effects given both groups will receive PC 	 Utilize evidence-based PC intervention guide developed through multiple prior trials Measure number of PC intervention visits and visit duration using electronic PC clinician encounter survey Measure number of in-person PC visits in the telehealth group and telephone visits in the in-person group

Training	 Development of PC intervention guide and videos Initial in-person training of lead site investigators on PC intervention and use of telehealth Initial in-person training of site research team members on study procedures and use of telehealth Onsite training at each participating site with all PC clinicians providing care to study patients Quarterly conference calls (led by Drs. [name] & [name]) with site investigators to address study issues Monthly conference calls (led by [name]) with the research team to address study procedures Annual retraining seminar via video conferencing with lead site investigators 	 Complete review of PC intervention guide and training videos Complete training of all site investigators in protocol administration, intervention delivery, and standardized material Complete training of research team members on study procedures, protocol and use of technology Assess pre- and post-knowledge that PC clinicians and research team members acquired during training Send meeting minutes from conference calls to all lead site investigators Send meeting minutes from conference calls to all site research team members Assess pre- and post-knowledge that lead site investigators acquired during retraining

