5.2. In-Person PC Arm

Patients randomized to in-person PC are scheduled for their first PC visit within four weeks of enrollment and then at least every four weeks thereafter until the patient is no longer able to come into the clinic or death. PC visits are scheduled on the same day as oncology visits unless the patient is agreeable to scheduling the PC visit on a different day. Joint visits with PC and oncology (i.e., both clinicians seeing the patient together in one visit) are recommended but not required. PC clinicians can see patients more often than every four weeks at their discretion. If a patient does not have a scheduled visit to the cancer center, the PC clinician contacts them through telephone within four weeks of their prior appointment to conduct the visit.

6. Modifications to Study Conduct during the COVID-19 Pandemic

The US health care response to COVID-19 was to rapidly minimize in-person care delivery in outpatient clinics, including oncology and palliative care. By March 10, 2020 nearly all health care systems were swiftly transitioning to predominantly telephone and video care models to minimize patient and clinician risk of COVID-19 infection. On March 15, 2020, study enrollment was closed to avoid significant contamination of the intervention delivery modality between study groups. From March 15, 2020 until May 2020, all REACH PC sites remained closed to enrollment. While REACH PC was closed to enrollment, all currently enrolled patients continued to complete patient-reported measures remotely, which was permitted as per the protocol prior to COVID-19, and to receive the intervention with monthly contact with a palliative care clinician. During this time, the majority of patients assigned to the in-person group received palliative care via telephone or video, which was closely documented in order to address such intervention contamination in the analytic plan.

7. Outcome Measures

The study outcome measures include a combination of participant self-report questionnaires and data from patients' electronic health records. The self-report measures are described in Table 1.

Name of Measure	Participant	Time points	Scoring
Sociodemographic Questionnaire	Pt & Cg	BL only	
SCQ	Pt only	BL only	Range: 0-36 (Higher
			score indicate worse
			medical condition)
FACT-L	Pt only	BL, 12, 24, 36, and 48	Total score range: 0-
		weeks	136 (Higher score
			indicates better
			quality of life)
Patient PTPQ	Pt only	BL, 12, 24, 36, and 48 weeks	

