The primary outcome is patient-reported quality of life at week 24, as measured by the FACT-L. The difference in week 24 means between intervention groups will be estimated using a linear regression model with group assignment (telehealth PC vs in-person PC) and baseline FACT-L score as main effects. Using the pre-specified equivalence margin of ±4 points, equivalence of telehealth PC will be established if the 90% confidence interval (CI) for the estimated difference in means is within the equivalence interval (-4, 4). The corresponding p-value for equivalence will be calculated as the larger of the two p-values from two one-sided tests of the estimated difference in means against null values of -4 and 4. Model-based estimates of the mean with 95% CI in each group, the difference in means between groups and its 90% CI, and the p-value will be reported.

To accompany the approach described above, we will also use a linear mixed effects regression model to estimate the difference in week 24 means between intervention groups. This model will

utilize FACT-L scores at baseline, week 12, and week 24, with estimation via maximum likelihood. The model will include fixed effects for group assignment (telehealth PC vs in-person PC), time from baseline (in weeks), and the time-by-group interaction, as well as random intercepts for each patient. A contrast will be used to estimate the difference in means at week 24, and this estimate will be evaluated for equivalence in the same manner described above. This will be reported as a sensitivity analysis for evaluating equivalence for the primary outcome.

Secondary Outcomes

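### Should the SAP have fixed one COVID-19 contamination analysis and said how telephone visits in the in-person arm are classed?

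*SAP*

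**What the plan says.** SAP section 9, under Analysis Population, makes intention-to-treat primary and then commits to further work: "To address intervention contamination introduced during the COVID-19 pandemic, sensitivity analyses will be conducted to ensure the validity of the study findings". The next sentence names the candidates without choosing among them: "These sensitivity analyses may include per-protocol analysis, contamination adjusted intention-to-treat analysis using instrumental variables, and inverse probability weighting analyses". It says they serve the primary and secondary outcomes.

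SAP section 6 explains why. Enrollment closed from 15 March 2020 until May 2020, and in that time most in-person patients "received palliative care via telephone or video, which was closely documented in order to address such intervention contamination in the analytic plan".

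Telephone contact is also part of ordinary care in that arm. SAP 5.2: "If a patient does not have a scheduled visit to the cancer center, the PC clinician contacts them through telephone within four weeks". Protocol 5.3.3 agrees: "If patients do not have a scheduled visit to the cancer center the PC clinician will contact them via telephone within four weeks". Protocol 5.3.4 adds, for either arm after a missed visit that cannot be rescheduled in time, that "the PC clinician will attempt to contact them via telephone within seven days from the missed visit to conduct a visit via telephone". The fidelity table in Protocol 5.5.3 plans to "Measure number of in-person PC visits in the telehealth group and telephone visits in the in-person group".

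SAP section 10 judges the primary model by its 90% interval against (-4, 4). Of the mixed-model sensitivity analysis it says "this estimate will be evaluated for equivalence in the same manner described above". It adds no such sentence for the contamination analyses, and the SAP addendum does not mention contamination.

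**The concern.** If in-person patients are in effect given remote care, a real difference between the two modalities shrinks in the intention-to-treat comparison. In a superiority trial that counts against the hypothesis; here it can count in its favour. The contamination analyses are the only ones aimed at this, yet the SAP leaves open which are run, what exposure means and who is per protocol.

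The telephone visit makes this concrete. An in-person patient phoned in April 2020 because no clinic visit was scheduled can be read as treated per protocol under SAP 5.2, or as contaminated under SAP 6. A per-protocol analysis could therefore keep or drop the same patients. With several methods and two classings, a reader could fear that only the favourable result would be shown.

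**Working it through.** **1. The plan's own figure.** Inputs: margin 4, true difference 0, 469 per group, two one-sided tests at 0.05 (SAP 8 and 9); SD 17.0 (Protocol 7.4) or 17.5 (SAP 8). With SE = SD × √(2/469), power = 2Φ(4/SE − 1.645) − 1.
- SD 17.0: SE = 1.110, power = 95.0%, the stated value.
- SD 17.5: SE = 1.143, power = 93.6%. This is used below as the more cautious value.

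**2. Effect of dilution.** Let c be the share of in-person follow-up time to week 24 that was in effect telehealth, and D the true modality difference. The intention-to-treat difference is then (1 − c)D, and

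P(declare equivalence) = Φ((4 − (1 − c)D)/SE − 1.645) − Φ((−4 − (1 − c)D)/SE + 1.645).

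| c | D = 4 | D = 6 |
|---|---|---|
| 0 | 5.0% | 0.03% |
| 0.01 | 5.4% | 0.04% |
| 0.02 | 5.8% | 0.05% |
| 0.05 | 7.1% | 0.09% |
| 0.10 | 9.8% | 0.2% |
| 0.20 | 17.2% | 1.0% |

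Six points is the bottom of the clinically meaningful range in Protocol 7.4.

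**3. How large c might be.** The documents give no accrual dates, so these are assumptions: uniform accrual; start between January 2018 and 24 weeks before closure; end between 7 March 2023 (48 weeks before addendum entry 3(A)) and 2 August 2023 (24 weeks before addendum entry 1); closure of 47 to 77 days, that is w = 6.7 to 11.0 weeks. Accrual time without the closure is T = 168 to 285 weeks.
- In-person patients within 24 weeks of enrollment at closure: 625 × 24/T = 53 to 89, or 8% to 14%.
- If all were moved to remote care for the closure only: c = (24w − w²/2)/(24T) = 0.020 to 0.050. If half were: 0.010 to 0.025.
- If remote care in the in-person arm lasted 24 weeks from 15 March 2020, also covering patients enrolled after reopening: c = 0.055 to 0.106, and 7.3% to 10.1% at D = 4. If it lasted 52 weeks: c = 0.15 to 0.26, and 13% to 23%. Neither duration is documented.

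**4. What the choice of method and classing changes.** Take the closure-only case at D = 0.
- Per protocol: dropping 8% or 14% of the in-person group (431 or 403 against 469) gives power 92.5% or 91.5%; keeping them gives 93.6%.
- Instrumental variable: dividing the estimate and SE by 1 − c at c = 0.02 to 0.05 gives power 92.6% to 90.7%, and a 90% half-width of 1.92 to 1.98 against 1.88.

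In that case the open choices cost at most about 3 percentage points of power.

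**5. The texts side by side.** Section 9 limits the contamination to what the pandemic introduced, and section 6 describes a wholesale switch during the closure. SAP 5.2 and Protocol 5.3.3 cover a patient with no clinic visit scheduled; Protocol 5.3.4 covers a missed visit. A permitted exception and a pandemic-wide switch can both stand. The fidelity table already counts telephone visits in the in-person arm while the protocol allows them. Video is no part of the in-person arm's procedure in any section, so only telephone visits need a classing rule.

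**The case for a change.** The strongest case for a change is that dilution runs toward the hypothesis, that these analyses are the only guard against it, and that open wording would let selective reporting pass unseen. Nor can the size be called securely small: accrual dates and the length of remote care are unknown, and a year of remote care would take the error at the margin to between 13% and 23%.

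Two parts of this stand. The SAP lacks an operational definition of exposure and of the per-protocol set, and the size cannot be fixed from the documents.

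The rest is weaker. The analyses are required; only the method is left open, in the same form of wording that section 9 uses for missing data. They are analyses of outcomes whose margins are set in section 10, so an estimate of the week-24 FACT-L difference has nothing else to be read against. The mixed model has its own sentence on the margin because it is fully described there. The dilution model also counts a telephone call as full receipt of telehealth, whereas Protocol 5.3.2 makes that arm video with telephone as a fallback, so the pull toward zero is itself assumed. Finally, addendum entry 3(B) answers peer review. Choosing one method now would be post hoc and would not bring the protection of pre-specification.

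**Conclusion.** No change to the plan is needed. This is missing operational detail in supportive analyses, not conflicting text and not a flaw in the primary test. Intention-to-treat, one model, one interval and one margin are fixed, and contamination analyses must accompany them. Stating which were run, how pandemic telephone and video visits were classed, and where each interval lies against (-4, 4) is ordinary reporting. The data for it are already collected: visit type in the post-visit survey (Protocol 5.4.2), chart notes where the survey is missing (Protocol 5.3.4) and the planned fidelity counts (Protocol 5.5.3).

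On the closure-only assumptions the error at a true difference of 4 rises from 5.0% to between 5.4% and 7.1%, and at 6 points it stays below 0.1%. This rests on assumed uniform accrual between assumed dates, on remote care ending with the closure, and on telephone care counting as telehealth. Longer remote care would give larger figures. It would make the required analyses more informative, but they are already in the plan.
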